Patients will be followed both clinically and radiographically (CT) at baseline then every 8 weeks after starting the treatment. Responses will be assessed using RECIST 1.1 criteria. Dose level 1 (4000 µg) will be the starting dose in the standard 3+3 dose escalation design. Three patients will be recruited for Dose level 1.

The next three patients will be recruited for Dose level -1 (2500 µg). While none of the three patients in Dose level 1 experienced a DLT, there were significant side effects. If 0 of three patients at Dose level -1 experiences a DLT related to SLM, then dose escalation will proceed to the next dose level (3000 µg).

If one of the three patients at Dose level -1 experiences a DLT related to SLM, then three more patients will be treated at the same dose. If exactly one out of six patients experiences a DLT, then dose escalation will proceed to the next dose level (3000 µg) after discussion at the weekly SLM meeting.

If two of the first three patients experience DLT related to SLM, then the dose will de-escalate to the lower dose (1500 µg).

The next patient can be enrolled after the previous patient's 28th Day of SLM assessment, provided there are no DLTs related to SLM. The minimum number of patients required is 6 and the maximum is 12.

Dose Limiting Toxicities:

DLTs related to SLM will be defined as any of the following events determined by the Investigator to be related to treatment combination irrespective of outcome. This applies to the first cycle only (2 weeks SLM alone + 4 weeks combination therapy):

- Clinically significant non-hematologic toxicity of Grade 3 or greater not related to underlying malignancy.
- Severe hematological toxicity (Grade 4 neutropenia, Grade 3-4 febrile neutropenia, or Grade 4 thrombocytopenia).
- If resolution of DLT related to SLM does not occur in 4 weeks, then patient will be withdrawn from the study.
- Grade 4 nausea, vomiting, diarrhea, or electrolyte imbalances or Grade 3 nausea, vomiting, diarrhea and electrolyte imbalances lasting greater than 48 hours despite optimal medical intervention.
- In the dose escalation phase, treatment delays related to the study drug that last >2 weeks

- Any grade 3 or higher DLT related to SLM alone will be discussed at the weekly SLM committee meeting.
-

Expansion Part 2: Enrollment Completed

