5.3 SLM AND AXITINIB ADMINISTRATION

SLM oral capsules will be given twice daily alone for the first 14 days, then once daily in combination with Axitinib thereafter. SLM dosing will be based on patient BSA for the Pilot phase and tolerance based on DLT assessments during run-in only. See section 14.4 for dosing information for the Pilot portion. SLM will be provided by the study free of charge, by Sabisna Corporation located in NJ, USA. SLM will be stored in the Investigational Pharmacy at University of Iowa Hospitals and Clinics.

Axitinib oral tablets will be provided by the study free of charge from Pfizer and stored in the Investigational Pharmacy at the University of Iowa Hospitals and Clinics. Dosing will start at 5 mg twice daily, with the two doses taken 12 hours apart, with or without food. Axitinib will begin after the patient completes the 14 day SLM run-in portion of the trial.

Over the course of treatment, patients who tolerate Axitinib for at least two consecutive weeks with no adverse reactions >Grade 2 (according to the Common Toxicity Criteria for Adverse Events [CTCAE]) may have their dose increased as follows.

When a dose increase from 5 mg twice daily is recommended, the Axitinib dose may be increased to 7 mg twice daily, and further to 10 mg twice daily using the same criteria.

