Dose escalation for this pilot study will be conducted using a continual reassessment method (CRM) in which the probability of exceeding a blood selenium concentration of 45 μM on Day 14 is being modeled. Prior probabilities of exceeding a blood selenium concentration of 45 μM on Day 14 were estimated based on preclinical and preliminary data from the initial trial. A one parameter logistic model with intercept set at 3 and an initial value of 1 for the slope will be used to estimate the dose-concentration relationship through sequential recursive Bayesian assessment. The target probability of exceeding 45 μM is $\leq 20\%$.

BSA	Dose Level ^a				
	1	2	3 ^b	4	5
1.50-1.79	2000	3000	4000	5000	6000
1.80-2.19	3000	4000	5000	6000	7000
2.20-2.49	4000	5000	6000	7000	8000
π_{45}^c	0.001	0.01	0.10	0.20	0.30

^aAll doses are mcg BID Day 1-14 then daily until progression.

^bStarting dose level.

^cProbability of exceeding 45 μM (prior)

[figure not shown]
Dosing will begin at dose level 3. Each cohort will enroll 2 evaluable patients. After each patient has completed the Day 14 evaluation, the following information will be provided to the statistical research team:

1. Blood selenium concentration on Day 14
2. DLTs, defined as any of the following treatment-related events occurring between Day 1 and 14 irrespective of outcome:
 - a. Clinically significant non-hematologic toxicity of Grade 3 or greater not related to underlying malignancy.
 - b. Severe hematological toxicity (Grade 4 neutropenia, Grade 3-4 febrile neutropenia, or Grade 4 thrombocytopenia).
 - c. Grade 4 nausea, vomiting, diarrhea, or electrolyte imbalances or Grade 3 nausea, vomiting, diarrhea and electrolyte imbalances lasting greater than 48 hours despite optimal medical intervention.

At which time, the dose-concentration model will be updated to obtain the recommended dose level for the subsequent cohort. Dose escalation will proceed one dose level at a time; skipping dose levels is not permitted.

Simulations

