Additional Safety Considerations

Preliminary data from the initial trial demonstrated the doses explored thus far were safe. In the Phase I dose-finding study of selenium in combination with irinotecan, all dose levels (max 7,200 mcg) evaluated were found to be safe but the upfront selenium run-in period was a week shorter than the current proposed dosing schedule (BID for 7 days vs BID for 14 days). As an additional safety precaution, patient accrual will pause if any DLTs are evidenced between Day 1 and 14 until the data and safety monitoring committee (DSMC) have reviewed the events and the appropriate course of action has been determined.

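### In the pilot, the dose-level update and the DLT pause use only Days 1-14 on SLM alone; the DLT criteria and the pause should also cover Days 15-42, when axitinib is being taken

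*Combined protocol and SAP*

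**What the plan says.** **Pilot phase**
- Section 14.4, Continual Reassessment Method: the model concerns only the probability that Day 14 blood selenium exceeds 45 µM. After each patient's Day 14 evaluation the statisticians receive the selenium level and the DLTs, which are "DLTs, defined as any of the following treatment-related events occurring between Day 1 and 14 irrespective of outcome". Then: "At which time, the dose-concentration model will be updated to obtain the recommended dose level for the subsequent cohort". DLTs are reported but do not enter the model.
- Section 14.4, Additional Safety Considerations: "patient accrual will pause if any DLTs are evidenced between Day 1 and 14", until the DSMC has reviewed the events.
- Section 5.3: pilot dosing depends on BSA and "tolerance based on DLT assessments during run-in only". It adds: "Axitinib will begin after the patient completes the 14 day SLM run-in portion of the trial". By footnote a of the pilot dose table, the assigned dose then continues once daily until progression, which means with axitinib.
- Section 7.0: the only DLT row concerns the run-in. For grade 3-4 non-hematologic toxicity, SLM is held but not reduced.

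**Part 1 (section 5.1)**
- The next patient waited for the previous patient's "28th Day of SLM assessment, provided there are no DLTs related to SLM".
- DLTs were counted over two weeks of SLM alone plus four weeks of the combination.
- Section 2.3 lists Part 1 doses of 2500 to 4000 mcg. The expansion used 4000 mcg.

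**Trial-wide**
- Section 7.1 suspends assignment, pending sponsor and DSMC review, when at least 10% of patients, evaluated cumulatively every 3 months, have attributable grade 3 or higher toxicity not controlled within 14 days of supportive care.
- Appendix B sends SAEs to the DSMC within 24 hours and has cumulative events compared with the stopping rules.

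**The concern.** The pilot dose is chosen on SLM alone but is taken with axitinib until progression, and the first primary objective is the safety of the combination. Under the rules in 14.4, a treatment-related DLT on, say, Day 20 neither pauses accrual nor holds the next cohort at the current level.

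Part 1 had that protection at lower doses, and tolerability there was not trivial. Section 5.1 reports: "While none of the three patients in Dose level 1 experienced a DLT, there were significant side effects". The next three patients were given 2500 mcg. At stake is whether later pilot patients can be moved up a level while a combination DLT at the level below goes unreviewed.

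**Working it through.** **1. Pilot doses against the 4000 mcg maximum given with axitinib** (dose table in 14.4)

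| Level | BSA 1.50-1.79 | BSA 1.80-2.19 | BSA 2.20-2.49 | Cells above 4000 |
|---|---|---|---|---|
| 1 | 2000 | 3000 | 4000 | 0 |
| 2 | 3000 | 4000 | 5000 | 1 |
| 3 (start) | 4000 | 5000 | 6000 | 2 |
| 4 | 5000 | 6000 | 7000 | 3 |
| 5 | 6000 | 7000 | 8000 | 3 |

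All levels: 0 + 1 + 2 + 3 + 3 = 9 of 15. Levels 3-5: 2 + 3 + 3 = 8 of 9.

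Per m², the starting level is at most 5000/1.80 = 2778 mcg/m². A fixed 4000 mcg at BSA 1.50 is 4000/1.50 = 2667 mcg/m², so the start is only slightly higher. The smallest level 4 dose is 6000/2.19 = 2740 mcg/m², so every level 4 dose exceeds 2667.

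**2. Combination days required**
- Pilot, before the next cohort: 14 - 14 = 0.
- Part 1, before the next patient: 28 - 14 = 14.
- Part 1 DLT window: 2 + 4 = 6 weeks (42 days), 28 of them on the combination.

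**3. Does the Day 14 selenium level stand in for later exposure?** Section 2.3 gives these cohort averages (units assumed to be µM):

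| Cohort | Day 14 | Cycle 2 | Cycle 7 | C2/D14 | C7/D14 |
|---|---|---|---|---|---|
| 1 | 30 | 44 | 104 | 1.47 | 3.47 |
| 2 | 14 | 21 | 25 | 1.50 | 1.79 |
| 3 | 17 | 25 | 43 | 1.47 | 2.53 |
| 4 | 17.5 | 27 | 64 | 1.54 | 3.66 |

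Levels keep rising after Day 14. If the Cycle 2 ratios hold, the 35-45 µM Day 14 target becomes about 35 × 1.467 = 51 to 45 × 1.543 = 69 µM at Cycle 2. Cycle 7 values may reflect only patients still on treatment.

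**4. What would trigger the 10% rule after two pilot cohorts (4 patients)?** Earlier patients number 6 + 19 = 25 to 12 + 19 = 31.
- Whole trial, no earlier qualifying event: 10% of 29 is 2.9, so 3 of the 4; 10% of 35 is 3.5, so all 4.
- Whole trial, 3 earlier events among 31: 4 are needed in total, so 1 of the 4.
- Pilot alone: 10% of 4 is 0.4, so 1 of the 4.

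The text does not say which denominator applies.

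**5. Illustration.** The documents give no combination DLT rate. For an assumed Day 15-42 risk p, the chance of at least one such DLT in a cohort of 2 is 1 - (1 - p)²: 19% for p = 0.10, 36% for p = 0.20 and 51% for p = 0.30. None of these events triggers the pause in 14.4.

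**The case against.** The Day 14 window is a stated choice. The pilot's own objective is the dose-concentration relationship, not an MTD, and a Day 14 endpoint suits it. That stands, and it is a reason to keep the CRM and its endpoint. It is not a reason to leave combination DLTs outside the pause.

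Other protections exist. The 10% rule has no Day 14 limit and on some denominators is met by one pilot event; SAEs reach the DSMC quickly. So a reader who infers that combination toxicity goes unmonitored, or that nothing could stop the next cohort, goes beyond the documents. What remains is that the 10% rule is evaluated every 3 months and counts only uncontrolled events, and that SAE reporting does not itself hold a cohort.

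The dose contrast can also be overread. Dosing is by BSA, Part 1 BSAs are not given, and the starting level is close to earlier exposure per m². The daily SLM dose halves when axitinib begins, although blood levels go on rising. Part 1 returned to 4000 mcg in its fourth cohort, and 14.4 describes the doses explored so far as safe. It also calls doses up to 7200 mcg with irinotecan safe, but that was another partner drug with a twice-daily phase one week shorter.

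Finally, zero combination days is a formal minimum. At the expansion's planned pace of 19/18, about 1.06 patients per month, some combination experience would usually exist before the next cohort. No rule in 14.4 requires anyone to use it.

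**Conclusion.** The concern holds as a gap in the pilot's stopping rules. The dose update and the DLT pause need 0 combination days, where Part 1 required 14 before the next patient and counted DLTs over 42 days. Most dose cells at levels 3-5 (8 of 9) exceed the highest SLM dose previously given with axitinib. The one other suspension rule is narrower, slower and unclear in its denominator.

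Two stronger readings are not supported. One is that the pilot would take selenium beyond anything seen on the combination: the projected 51-69 µM at Cycle 2 lies within cohort averages already reached at Cycle 7 (64 and 104), although those come from few patients. The other is that escalation must wait for both patients to reach Day 42: that is stricter than Part 1's own Day 28 wait and would depart from the cohort flow simulated in 14.4.

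The dose counts describe table cells; the share of patients above 4000 mcg depends on BSA. The 19%, 36% and 51% rest on assumed risks and only illustrate scale. This is a cheap safety improvement that should be made, not a flaw in the concentration analysis.

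**What to change.** - **Section 14.4:** keep the CRM, the Day 14 concentration endpoint and the cohort flow. Apply DLT criteria a to c, and the accrual pause with DSMC review, to Days 15-42 as well, for events attributed to SLM or the combination but not to axitinib alone. Align the run-in-only wording in 5.3. The run-in DLT row in 7.0 can stay as it is, so later events are managed in the individual patient as now.
- **Section 14.3.1a:** if pilot DLTs are tabulated there, show Days 1-14 (SLM alone) separately from Days 15-42 (combination).
- **Optional stricter step:** match Part 1 by opening a higher level only after patients at the current level reach Day 28 of SLM.

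**Cost.** A protocol amendment for the remaining pilot cohorts; the documents do not mark pilot enrollment as complete. Cycle 1 visits and adverse event recording already exist, so no visits, tests or patients are added. The downside is an occasional accrual pause. The optional step adds up to 28 - 14 = 14 days per upward step. Five cohorts starting at level 3 leave four moves and at most 3 upward steps (for example 3, 2, 3, 4, 5), so at most 3 × 14 = 42 days. If patients are added at the current level while waiting, the CRM simulations need a check.

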Consequently, only a small sample would be required. To justify our sample, we will be operating under the assumption that the median survival will increase to 14 months in our treated population and that 90% upper confidence intervals will be constructed for the PFS (which would be equivalent to testing at 10% significance level, if statistical tests were to be carried). This may not be a stone-cut hypothesis; but reasonable for pilot justification. For the statistical analysis, exponential survival will be assumed and the associated survival rate estimated with maximum likelihood methods. A Wald statistic will be used to test this imperfect null hypothesis that median survival is equal to 8 months versus the one-sided alternative that it is greater than 14 months. With the planned enrollment of 19 patients accrued over 18 months and a total follow up for 14 months. The study will have 80% power to detect an increased survival of 6 months. The reason for this power justification is to put things into perspective and give an idea that one can actually glean some information out of this study—information that will serve as hypothesis generating for a larger trial. Estimates will be reported along with confidence intervals.

Pilot phase: Extra cohort with BSA based dose:

The primary objective of this pilot dose-finding study is to characterize the dose-concentration relationship and estimate the effective administered dose of selenium necessary to achieve the target blood concentration range informed by preclinical data. Preliminary data from the initial trial indicate a single fixed dose of selenium conferred significant variability in patient blood selenium concentrations at the end of the 14-day run-in. Patient body surface area (BSA) was found to be a contributing factor with patients of lower BSAs more frequently having higher blood selenium concentration, although none of which were within the targeted range of 35-45 μM . In light of these findings, a modified dosing scheme is being investigated which varies the dosage of selenium by BSA within a dose level to ensure less variability in the dose per m^2 administered.

Continual Reassessment Method

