Simulations were conducted to evaluate the performance of the proposed design across various scenarios. More specifically, several potential underlying truths of the dose-concentration profiles were considered, and how the trial behaved in each of those scenarios was evaluated. Scenarios under consideration are those represented in the figure and table below. For each of the scenarios, simulations are based on the following specifications: cohorts of size 2 will enter the trial, a total of 10 patients will be used for each simulation, 1000 Monte Carlo replications are used, a one-parameter logistic model with starting parameter of 3 for the intercept and an initial slope of 1, no skipping dose levels, and starting at dose level 3.

	Dose Level				
	1	2	3	4	5
True Scenario 1	0.001	0.001	0.001	0.010	0.050
True Scenario 2	0.001	0.010	0.050	0.100	0.200
True Scenario 3 (Prior)	0.001	0.010	0.100	0.200	0.300
True Scenario 4	0.001	0.010	0.150	0.300	0.400
True Scenario 5	0.001	0.010	0.200	0.400	0.500

$\pi_{45} \leq 20\%$ are in green and $>20\%$ in red.

The operating characteristic using simulations for each scenario are summarized below.

		Dose Level				
		1	2	3	4	5
True Scenario 1:	% Selection	0.00	0.20	0.30	2.20	97.30
	% Subjects Treated	0.04	20.24	20.26	20.76	38.70
	# Subjects Treated	0.00	2.02	2.03	2.08	3.87
	Average Toxicities	0.00	0.00	0.01	0.02	0.21
	True Probabilities	0.001	0.001	0.001	0.010	0.050
True Scenario 2:	% Selection	0.00	2.70	6.50	22.50	68.30
	% Subjects Treated	0.52	23.80	24.92	22.98	27.78
	# Subjects Treated	0.05	2.38	2.49	2.30	2.78
	Average Toxicities	0.00	0.02	0.12	0.23	0.56
	True Probabilities	0.001	0.010	0.050	0.100	0.200
True Scenario 3:	% Selection	0.00	4.30	20.00	31.50	44.20
	% Subjects Treated	0.62	25.74	29.82	24.32	19.50
	# Subjects Treated	0.06	2.57	2.98	2.43	1.95
	Average Toxicities	0.00	0.02	0.30	0.48	0.59
	True Probabilities	0.001	0.010	0.100	0.200	0.300
True Scenario 4:	% Selection	0.00	7.20	33.70	36.30	22.80
	% Subjects Treated	0.74	28.50	34.00	22.76	14.00
	# Subjects Treated	0.07	2.85	3.40	2.28	1.40
	Average Toxicities	0.00	0.02	0.49	0.65	0.60
	True Probabilities	0.001	0.010	0.150	0.300	0.400
True Scenario 5:	% Selection	0.10	13.00	48.20	27.60	11.10
	% Subjects Treated	1.34	32.94	36.02	21.36	8.34
	# Subjects Treated	0.13	3.29	3.60	2.14	0.83
	Average Toxicities	0.00	0.03	0.70	0.86	0.41
	True Probabilities	0.001	0.010	0.200	0.400	0.500

$\pi_{45} \leq 20\%$ are in green and $>20\%$ in red.

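### The pilot CRM operating-characteristics table does not describe the stated design: dosing is said to start at level 3, but the printed patient counts are those of a level-2 start

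*Combined protocol and SAP*

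**What the plan says.** The start level is given three times in section 14.4. Under Continual Reassessment Method the text says "Dosing will begin at dose level 3", and footnote b of the dose table marks level 3 as the start. Under Simulations the settings include "no skipping dose levels, and starting at dose level 3".

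The other settings needed here are also in section 14.4:

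- Size: "cohorts of size 2 will enter the trial, a total of 10 patients will be used for each simulation".
- Replications: "1000 Monte Carlo replications are used".
- Escalation: "Dose escalation will proceed one dose level at a time; skipping dose levels is not permitted".
- Model: one-parameter logistic, intercept 3, initial slope 1, with prior risks 0.001, 0.01, 0.10, 0.20 and 0.30 of exceeding 45 µM at levels 1 to 5, and a target of at most 20%.

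After each cohort "the dose-concentration model will be updated to obtain the recommended dose level for the subsequent cohort". The section does not give the slope prior or the estimator. It does not say whether the next level is the one nearest 20% or the highest at or below 20%.

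**The concern.** In Scenario 1 the true risks are 0.001, 0.001, 0.001, 0.010 and 0.050. Two patients treated at level 3 almost never exceed 45 µM, so a trial starting there has no reason to visit level 2. Yet the table prints 2.02 patients at level 2, one full cohort. Every scenario prints at least 2.02 there (2.02, 2.38, 2.57, 2.85, 3.29), as expected if the first cohort is always treated at level 2.

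The table is the protocol's own evaluation of how the proposed design behaves. If it was produced from a lower start, a reader judging exposure at the upper levels is looking at a gentler design than the one written down. Level 5 is 6000–8000 mcg BID for 14 days. The earlier irinotecan combination study reached 7200 mcg with only 7 days of BID loading.

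**Working it through.** **1. The printed rows are internally consistent.** Mean patients times true risk should give the Average Toxicities row. For Scenario 5, levels 3 to 5: 3.60 × 0.200 = 0.72, 2.14 × 0.400 = 0.86, 0.83 × 0.500 = 0.41; printed 0.70, 0.86, 0.41. The columns have not shifted.

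**2. Bound that needs no slope prior (Scenario 1, level-3 start).** Assume only that the rule steps down after an exceedance and not otherwise, and that levels are not skipped upwards. The path with the most exceedances is 3-4-5-5-5. Send every remaining patient to level 2 or below at the first exceedance:

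| Cohort | Level | Probability of first exceedance here | Patients left |
|---|---|---|---|
| 1 | 3 | 1 − 0.999² = 0.0020 | 8 |
| 2 | 4 | 0.998 × (1 − 0.99²) = 0.0199 | 6 |
| 3 | 5 | 0.978 × (1 − 0.95²) = 0.0954 | 4 |
| 4 | 5 | 0.883 × (1 − 0.95²) = 0.0861 | 2 |

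Maximum at levels 1–2 = 8(0.0020) + 6(0.0199) + 4(0.0954) + 2(0.0861) = 0.69 patients. The SD per trial is 1.50, so the standard error over 1000 trials is 0.047. The printed 20.24% is 2.024 patients, and (2.024 − 0.69)/0.047 ≈ 28.

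**3. Path check without the step-down assumption.** Suppose instead only that levels are not skipped in either direction. In 0.999² = 99.8% of Scenario 1 trials the first cohort has 0/2 exceedances, so the model sends all of these to the same next level.

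| Next level(s) after clean cohorts | Consequence | Printed |
|---|---|---|
| 2 | level 5 at most 0.998×2 + 0.002×6 = 2.01 | 3.87 |
| 3 | level 3 at least 2 + 2×0.998 = 4.00 | 2.03 |
| 4, then 3 | level 3 at least 2 + 2×0.978 = 3.96 | 2.03 |
| 4, then 4 | level 4 at least 2×0.998 + 2×0.978 = 3.95 | 2.08 |
| 4, then 5 | level 2 at most 8×0.002 + 4×0.0199 = 0.10 | 2.02 |

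No branch gives the printed row.

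**4. Which start does fit?** The CRM was enumerated exactly (5 cohorts of 2, intercept 3, dose labels from the printed prior risks at slope 1, no upward skipping). The unstated parts were varied:

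- six slope priors: exponential(1); gamma with mean 1 and shape 2 or 4; log-normal with median 1 and log SD 0.5 or 1.16; uniform(0,3)
- two estimators: plug-in posterior mean slope, or posterior mean probability
- two rules: nearest 20%, or highest at most 20%
- downward skipping allowed or not

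That makes 48 variants per start level. Scenario 1 patients at level 2 are 0.00–0.06 in all 48 from level 3, and 2.01–2.02 in all 48 from level 2.

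The best-fitting variant is exponential(1), plug-in, nearest 20%, downward skipping allowed. Its mean patients at levels 1–5 are:

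| Scenario | Printed | Level-2 start | Level-3 start |
|---|---|---|---|
| 1 | 0.00/2.02/2.03/2.08/3.87 | 0.00/2.02/2.01/2.07/3.90 | 0.00/0.01/2.05/2.06/5.88 |
| 3 | 0.06/2.57/2.98/2.43/1.95 | 0.06/2.62/2.96/2.42/1.94 | 0.05/0.95/3.73/2.34/2.92 |
| 5 | 0.13/3.29/3.60/2.14/0.83 | 0.12/3.31/3.70/2.07/0.79 | 0.18/2.10/4.74/1.89/1.09 |

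From level 2 this variant is within 0.12 patients of all 25 printed counts and within 3.4 points of all selection percentages. From level 3, each of the 48 variants misses at least one count by 1.96–2.32 patients.

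**5. Size of the error for the stated level-3 start (range over the 48 variants).**

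| Scenario | Level-5 patients (printed) | Expected exceedances (printed total) | % selecting a level with true risk above 20% (printed) |
|---|---|---|---|
| 1 | 5.3–5.9 (3.87) | 0.29–0.32 (0.24) | none above 20% |
| 2 | 3.0–4.5 (2.78) | 1.04–1.30 (0.93) | none above 20% |
| 3 | 1.8–3.2 (1.95) | 1.39–1.89 (1.39) | 23–56 (44.2) |
| 4 | 1.1–2.0 (1.40) | 1.57–2.35 (1.76) | 23–55 (59.1) |
| 5 | 0.6–1.2 (0.83) | 1.63–2.69 (2.00) | 12–37 (38.7) |

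The lower ends for level-5 patients in Scenarios 1 and 2 need no prior if an exceedance-free record always moves up one level and then stays at 5. In Scenario 1 this gives 2(0.978 + 0.883 + 0.797) = 5.32; the same sum in Scenario 2 gives 3.00.

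**The case against.** The best case for leaving this alone is that little depends on the table. The level for actual dosing is unambiguous. During the trial the model updates on observed Day 14 concentrations, so no patient's dose comes from these simulations. Section 14.4 does not derive the 10 patients, the 20% target or any stopping rule from them. The toxicity safeguard, that "patient accrual will pause if any DLTs are evidenced between Day 1 and 14", is separate. Under the best-fitting variant no selection percentage moves by more than 5.8 points from print. All of this stands, and it limits the severity.

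The direction is also mixed. The printed table understates exposure at level 5 in Scenarios 1 and 2. But it overstates the chance of finally selecting a level above 20% risk in Scenarios 4 and 5 under all 48 variants, and Scenario 3 can go either way. The Scenario 2 understatement of exceedances depends on the model: if every remaining patient went straight to level 1 after an exceedance, the total could be as low as 0.88, below the printed 0.93. In Scenario 1 the floor is 0.29 even then.

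The 0.69 bound relies on the ban on upward skipping. The protocol states that ban, and with a jump from 3 to 5 the bound would still be only about 1.1.

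Finally, the prior-free checks exclude level 3 but do not prove level 2. That identification rests on the fit to the whole table. None of these points reconciles the table with its stated settings.

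**Conclusion.** The concern holds. The printed operating characteristics do not belong to the level-3 start stated in the text, the dose-table footnote and the simulation settings. Excluding level 3 needs no slope prior, only the no-skipping rule together with step-down after exceedances, or no skipping in both directions. The level-2 start is inferred, but closely: all 25 counts agree within 0.12 patients. The selection rule is inferred too. The best level-2 variant using the highest level at or below 20% stays within 0.44 patients but misses selection by 20.9 points.

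The practical size is moderate for exposure at level 5 (about 1.4 to 2.0 more patients in Scenario 1, 0.2 to 1.7 more in Scenario 2) and small for exceedances (under 0.4 per 10 patients in those scenarios). Results for Scenarios 3 to 5 depend on the unstated prior and rule. The table should be fixed, but the error does not endanger the conduct of the trial.

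The table addresses only the risk of exceeding 45 µM. It says nothing about the dose "necessary to achieve the target blood concentration range informed by preclinical data", which is the pilot's stated objective.

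**What to change.** Rerun the simulations from the start level the trial will use and replace the table. If level 2 was intended, correct the text, footnote b and the simulation settings instead. Alongside the new table, state the slope prior, the estimator, and whether the next level is the one nearest 20% or the highest at or below it, so that the table can be checked against the algorithm actually run. The choice of start level and rule is the sponsor's.

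The cost is a few hours of simulation and one replaced table, with no added patients. If level 3 stays, Scenarios 1 and 2 will show more patients at level 5 and probably more exceedances, while wrong final selection in Scenarios 4 and 5 should look somewhat better than printed.
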